3.5.1 Injections

If a patient receives a corticosteroid injection 90 days after enrollment, it is not possible to truly assess the study drug's ability to manage inflammation at the Month 6 visit. Therefore, as a sensitivity analysis, the primary outcome for these patients will be considered by the inflammation levels at the time of the injection. If the patient received the injection because of uncontrolled inflammation, the patient will be considered a treatment failure. If the patient met the definition of treatment success at the time of the injection, the patient will be considered a treatment success.

3.6 Pooling across sites

Approximately three-fourths of patients are expected to come from the [REDACTED] sites, which are in the same hospital network in the geographic region serving the same patient population. [REDACTED] serve slightly different populations, although we expect fewer cases overall in the U.S. sites.

3.7 Multiple comparisons

An alpha of 0.05 will be used for the primary analysis of Specific Aims 1 and the primary analysis of Specific Aim 2. The prespecified subgroup analyses of Specific Aim 1 will be conducted at an alpha level of 0.05 (as stated above) as well. However, the use of an overall test prior to subgroup analysis protects the overall type I error rate for the primary outcome, a procedure we apply within the analysis of each secondary outcome as well.

3.8 Interim Monitoring

The study will be monitored by a Data Safety Monitoring Committee (DSMC) appointed by the National Eye Institute. There will be one in-person meeting a year and additional phone calls as deemed necessary. The DSMC will be unmasked and receive reports with information by treatment arm from the principal statistician.

3.9 Accrual Rate

Based on enrollment rates in previous trials and preliminary data (see proposal for details) we anticipate enrolling 7-8 subjects per month at all sites, for a total enrollment period of 2.5 years. If we conservatively assume we may only accrue 25% fewer subjects per month, then completion of enrollment would occur 3 years and 3 months after the start of the trial.

We will establish monthly recruitment goals for each of the sites, taking into careful consideration local holidays which may cause recruitment rates to drop at certain times of the

year. Careful monitoring of the recruitment process will enable us to determine whether one of our sites may be falling behind in recruitment, precursory to further investigation and intervention. Standard graphs of realized cumulative recruitment together with cumulative recruitment goals for (a) the study as a whole, and (b) for each of the four sites will be prepared, and provided to the Data and Safety Monitoring Committee at each meeting (or more frequently, if requested).

3.10 Interim Analysis

We propose to conduct two interim analyses, at approximately one-third and at approximately two-thirds of the way through the study. The exact fractions will be determined by availability of data and timing of DSMB meetings. We plan to examine the primary outcome variable using the same statistical model we plan for the final analysis. A flexible alpha spending function is specified in Section 6.

3.10.1 Stopping rules

Stopping rules for benefit, harm, and futility are discussed in Section 6.2. These rules or guidelines would be determined at the first meeting of the DSMC (see Section 6.2).

3.10.2 Execution of interim analysis

The principal statistician [REDACTED] will conduct the interim analysis in an unmasked manner, subject to independent statistical review by the DSMC. Quality assurance will be conducted by database manager [REDACTED].

3.11 Final Analyses

The Primary Aim 1 analysis (and secondary objectives), identified in this Statistical Analysis Plan will be performed when all patients complete their 6 month assessment and the window period is completed. All other analyses will be completed after the 12 month visit for Phase I or 6 month visit for Phase II and window periods are complete.

3.12 Software

The standard software program R version 2.12 or higher (<http://www.r-project.org>) for the MacIntosh OS X will be used for all descriptive and inferential analyses.

4 Analysis Populations

4.1 Summary

The following analysis populations are planned for this study:

- The **screening population**, which is to include all patients who are screened for participation in the trial.

- The **safety population**, which is to include all patients who receive any amount of planned study medication (mycophenolate mofetil or methotrexate).
- The **intent-to-treat efficacy population**, which is to include all patients who are randomized. This is the primary population for the efficacy analyses.
- The **per-protocol efficacy population**, which is to include all patients in the intent-to-treat efficacy population, excluding patients with any of the following: (a) major protocol deviations, or (b) noncompliance with study medications (less than 50% of the study drug received by self report or pill counts at study visits).

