2.5. Definitions for primary endpoint

2.5.1. Determination of Treatment Success/Failure

Treatment success is defined as controlled ocular inflammation (see Table 2) in both eyes with 7.5 mg/day of prednisone, no periocular or intravitreal corticosteroid injections after the first 90 days of follow up, and ≤ 2 drops/day of topical 1% prednisolone acetate at the 6 month visit without treatment failure any point due to safety, tolerability or futility. Patients can stop medication at any time, but that in and of itself does not count as a treatment failure.

Table 2: Criteria for controlled inflammation

Parameter	Definition of control
Anterior chamber cells*	$\leq 0.5+$
Vitreous haze**	$\leq 0.5+$
Choroid & retina***	No active inflammation or retinal vasculitis posterior to the equator

*SUN criteria³⁰; ** NEI vitreous haze grading scale³¹ *** Cystoid macular edema is not sufficient to be called active inflammation

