2.5.3. Dropouts, Non-Compliant Patients and Follow-up

- **Dropout from study:** Patients will be considered to have dropped out from the study only if they **declare they are no longer interested in further participation and not willing to return for any study visits, or are deceased**. If patients are not willing to return for any study visits, no further information will be collected on those patients. We anticipate that a few patients may drop out due to unwillingness to continue or death. In case of patient dropout, the patient dropout form should be filled out.

[figure not shown]
If death is considered to be related to the study drug, the patient will be counted as a treatment failure. If death is not related to the study drug, the patient will be counted as a dropout. This would be at the discretion of the Medical Monitor.

- **Non-compliant Patients:** Patients who stop the study treatment for reasons other than efficacy, tolerability and/or safety (i.e. fear of potential side effects) but are willing to return for study visits, are not considered dropouts. Also, if patients miss study visits, and do not respond to contact, they are not considered dropouts. These patients will be considered **non-compliant patients**, and will be encouraged to return for subsequent study visits regardless of whether or not they are taking study medication, especially the 6 month visit (Phase I and Phase II).

It should be noted that missing a visit does not mean that a patient has dropped out of the study. These patients are considered to be non-compliant. For example, if they missed the 1 month visit, every attempt will be made to bring them back as soon as possible and to continue with subsequent visits. Also, a non-serious adverse event or discontinuation of study medication does not mean that the patient has dropped out and they should continue to be followed according to the protocol, as they may be able to resume treatment. Even if the patient is not willing to resume treatment, but is willing to return for study visits they are not considered dropouts.

- **Following Patients who fail prior to Phase I & Phase II (6 months):** If patients are declared a treatment failure prior to Phase I or Phase II 6 Months, every effort should be made to bring the patient back for the 6 month visit. Note, that patients who are declared treatment failure, and are switching from Phase I to Phase II will already be followed.

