- Baseline best spectacle-corrected visual acuity, vitreous haze, macular thickness
- Vasculitis

Inclusion of Data

- Data will be included for all outcomes within the window period of -2 weeks to +4 weeks around the 6 Month Visit date for Phase I (0-6 months).
- Data will be included for all outcomes within the window period of -2 weeks to +4 weeks around the 12 Month Visit date for Phase I (6-12 months).
- Data will be included for all outcomes within the window period of -2 weeks to +4 weeks around the 6 Month Visit for Phase II (0-6 months).

3.2.2 Specific Aim 1

Primary Analysis.

The primary analysis will be a logistic regression model, predicting treatment success at 6 months based on treatment arm. We wish to aggregate sites within countries, and countries within treatments provided we find no evidence of heterogeneity of sites or countries.

Specifically, the pre-specified primary analysis will be performed as follows. We denote the assignment group of patient i , $i=1, \dots, N$ (where N is the number of subjects) by X_p^1 which equals 0 when the patient is in the methotrexate group and 1 when the patient is in the mycophenolate mofetil group. The outcome variable is Y_p which is 1 if treatment success of patient i is achieved by six months, and 0 otherwise. The variable is missing if the patient is lost to follow-up or drops out of the study for reasons other than discontinuation due to intolerance or adverse events; if the patient discontinues the medication due to intolerance or adverse events such as abnormal laboratory findings, the value is 0.

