4. *Quality of life.* For a power calculation, we consider the SF-36 questionnaire, which has two scales, the MCS and the PCS. The raw score standard deviation will be assumed to be 8.4 points; we assume a correlation between baseline and six months of 0.6.^{16, 17} Assuming that the baseline score will “explain” roughly 36% of the variance allows us to assume a corrected raw score standard deviation of 6.72 in a simplified calculation in which we treat the analysis as a T-test. The same power calculation formula used in (3) above reveals that **our sample size provides approximately 80% power to detect a raw score difference of roughly 2.57 between the two treatment groups.** This difference is roughly comparable to the small difference in scores found between intermediate uveitis patients and the general population¹⁶, a difference we believe to be more than sufficient to detect clinically significant results. Note that the population mean of this score is standardized to 50 on 0 to 100 scale. Similar analyses will be conducted for the vision related quality of life (i.e. NEI-VFQ-25 and the IND-VFQ).

5. *Rate of discontinuation.* Based on retrospective studies, we expect approximately 13% to discontinue methotrexate due to tolerability and 5% to discontinue due to safety (laboratory abnormalities or other serious adverse events). We expect approximately 4% to discontinue mycophenolate mofetil due to tolerability and 5% to discontinue due to safety.^{12, 18-20} For the purpose of the power calculation, we assume 10% loss to follow-up and consider only the comparison of discontinuation due to tolerability. **We use the power formula given in Freedman et al (p. 104) to calculate a power of 61% for this comparison.**³

6. *Macular edema.* Previous studies suggest approximately 38% of individuals with uveitis will manifest macular edema.²¹ **We have approximately 80% power to detect a difference of a factor of two in the final proportion of macular edema (19% vs 38%).**

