4.2 Major protocol deviations

The incidence of deviations from the inclusion and exclusion criteria will be summarized using counts and percentages, and the treatment groups compared for the overall frequency of deviations using a $2 \times N$ Fisher's exact test. Similar deviations will be grouped into general categories of deviations for a more condensed summary. A listing of deviations by participant will also be produced. Any major deviations from the protocol will be listed and/or summarized, including, but not limited to, participants who:

- never received study drug
- were subsequently found to be ineligible for the study
- never returned for a follow-up visit
- have follow-up visits outside the prescribed visit window
- received a corticosteroid injection >90 days after enrollment for macular edema or at any time for inflammation

The number and percentage of randomized participants actually receiving study medication, permanently discontinuing study drug (subdivided by reason), and receiving injections >90 days past enrollment will be summarized. A summary of study participants randomized by site will also be provided. Treatment groups will be compared for the proportion and reason for study drug discontinuation using the chi-square test. A summary of participant status at the end of the study period will also be generated with categories including lost to follow-up.

5 Data Collection and Quality Assurance

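### The per-protocol efficacy population is partly selected on the primary outcome: late injections, and on a literal reading early declared failures, are both endpoint failures and grounds for exclusion

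*Combined protocol and SAP*

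**What the plan says.** SAP 4.1 makes the intent-to-treat population primary for efficacy. It also defines a per-protocol efficacy population, which drops patients on two grounds. One is a protocol deviation classed as major; the other is "noncompliance with study medications (less than 50% of the study drug received by self report or pill counts at study visits". The major-deviation list in SAP 4.2 includes patients who "received a corticosteroid injection >90 days after enrollment for macular edema or at any time for inflammation".

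Protocol 2.5.1 makes success at month 6 conditional on "no periocular or intravitreal corticosteroid injections after the first 90 days of follow up" and on no treatment failure at any earlier point for safety, tolerability or futility. SAP 3.2.2 (Primary Analysis) codes the outcome to match: "if the patient discontinues the medication due to intolerance or adverse events such as abnormal laboratory findings, the value is 0".

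Two further protocol statements bear on the 50% rule. Section 2.5.1 says "Patients can stop medication at any time, but that in and of itself does not count as a treatment failure". Section 2.5.3 applies the term non-compliant to "Patients who stop the study treatment for reasons other than efficacy, tolerability and/or safety" who are still willing to attend visits, and to patients who miss visits.

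For expected discontinuation, SAP 3.4.2 item 5 says "we expect approximately 13% to discontinue methotrexate due to tolerability and 5% to discontinue due to safety", and for the other arm: "We expect approximately 4% to discontinue mycophenolate mofetil due to tolerability and 5% to discontinue due to safety".

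**The concern.** A per-protocol set should be chosen on how treatment was delivered, not on how it turned out. Here one event, an injection after day 90, both decides the outcome and removes the patient from the denominator.

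The 50% rule may do the same. The protocol builds in early declared failures: intolerance in the first two weeks (3.1.1, 3.1.2), futility after non-response to the first weeks of treatment (3.2.1), and immediate stopping for a serious laboratory abnormality (5.6). Such a patient takes well under half of a six-month course. If the planned course is the denominator, the patient is deleted rather than counted as a failure.

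Deleting failures raises the success rate in both arms, and raises it more in the arm that loses more of them. The SAP expects more tolerability stops on methotrexate. A per-protocol comparison could therefore lose part of a real tolerability difference, and would lean toward finding methotrexate no worse. That conclusion has weight here, because SAP 3.2.2 item 16 plans a methotrexate non-inferiority analysis, motivated by cost, and does not name its population.

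**Working it through.** **1. Late injections (text only).** Protocol 2.5.1: an injection after day 90 means the patient is not a success. SAP 4.2: an injection after day 90 for macular edema or inflammation is a major deviation. SAP 4.1: major deviations leave the per-protocol set. The overlap needs no assumption. The documents give no expected rate, so its size cannot be computed.

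**2. When a stop falls under 50%.** Take a planned 26-week course as the denominator (an assumption, since the SAP states none), with the doses in protocol Table 4.
- Methotrexate: 2×15 + 24×25 = 630 mg; half is 315 mg, reached at week 2 + (315 − 30)/25 = 13.4.
- Mycophenolate: 14×1 + 24×7×3 = 518 g; half is 259 g, reached at week 2 + (259 − 14)/21 = 13.7.

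Only stops before about week 13 to 14 trigger the rule. The documents do not say how many stops are that early.

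**3. The SAP's own figure.** SAP 3.4.2 item 5 gives 61% power for 13% vs 4% tolerability stops. With n = 97 per arm (108 less 10%) and mean rate 0.085:

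Φ[(0.09·√97 − 1.96·√(2×0.085×0.915)) / √(0.13×0.87 + 0.04×0.96)] = Φ(0.29) = 61.5%.

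The figure reproduces, so the rates are being read as the SAP uses them.

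**4. Effect of deleting the stops.** Tolerability plus safety: methotrexate 13% + 5% = 18%, mycophenolate 4% + 5% = 9%. Of 97.2 assessable patients per arm these are 17.5 and 8.7. If a fraction d of an arm, all failures, is deleted, success s becomes s/(1 − d). The success pairs are the SAP's planning rates (40%/60%) and an assumed true equality (50%/50%), with methotrexate first. The half and quarter rows are assumptions. Differences are from unrounded values.

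| Stops before half-way | d, MTX / MMF | 40%/60% becomes | 50%/50% becomes |
|---|---|---|---|
| All | 18% / 9% | 48.8% / 65.9% (gap 17.2) | 61.0% / 54.9% (6.0 toward MTX) |
| Half | 9% / 4.5% | 44.0% / 62.8% (gap 18.9) | 54.9% / 52.4% (2.6 toward MTX) |
| A quarter | 4.5% / 2.25% | 41.9% / 61.4% (gap 19.5) | 52.4% / 51.2% (1.2 toward MTX) |

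**5. If the set were used for non-inferiority.** Assume true rates of 50% (methotrexate) and 60%, exactly at the 10-point margin, with 97.2 per arm before deletion. The chance that the lower 95% limit clears −10 points is Φ[(p₁ − p₂ + 0.10)/SE − 1.96], where SE = √(p₁(1 − p₁)/n₁ + p₂(1 − p₂)/n₂), and each p and n is taken after deletion.
- Nothing deleted: 2.5%.
- Half the stops deleted (54.9% vs 62.8%): 4.8%.
- All deleted (61.0% vs 65.9%): 10.0%.

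**6. A planned-dose denominator also catches adherent patients.** Full adherence at Reduction Level II (protocol Table 5) from week 2 gives 26×15 = 390 of 630 mg methotrexate (62%), but 26×7×1 = 182 of 518 g mycophenolate (35%). Such a mycophenolate patient would be excluded without having failed.

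**The case against.** The strongest reply is that the protocol already says what non-compliance means. Under 2.5.3 it is stopping for reasons other than efficacy, tolerability or safety. Carried into SAP 4.1, that meaning makes the 50% rule delete none of the declared failures. The protocol's adherence procedures (3.1.5), which rely on calendars and counts of pills remaining from the last study period, also suggest a measure against drug dispensed rather than against a full six-month course. This stands as a plausible reading. But SAP 4.1 gives its own definition in parentheses and does not refer to 2.5.3, so the two definitions conflict and either population could be built.

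A second reply is that excluding recipients of disallowed therapy is ordinary per-protocol practice, and SAP 3.5.1 says the drug's effect cannot truly be assessed after a late injection. That is fair as motivation. However, 2.5.1 has already settled how the primary endpoint scores such a patient; 3.5.1, which may rescore some of them as successes, is only a sensitivity analysis.

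A reader might infer several stronger things that the documents do not support:
- That stopping drug is itself a failure. Protocol 2.5.1 says it is not; only stops tied to intolerance, safety or futility are.
- That everyone excluded is a failure. The list in SAP 4.2 also covers ineligible patients, out-of-window visits and early injections for inflammation.
- That twice as many methotrexate patients will be deleted. The 18% and 9% are all tolerability and safety stops, not rates of taking under half the drug. The 2:1 ratio needs equal timing in the two arms and cannot be extended to injections or futility. Step 6 shows a force in the other direction.

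**Conclusion.** The concern holds in a limited form. For late injections, selection on the outcome follows from the text alone. For the 50% rule, it follows from a literal reading that the protocol's own definition contradicts; the passages must be reconciled.

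The size is bounded for tolerability and safety stops only: at most 6.0 points toward methotrexate at a true 50%/50%, or a 20-point planned gap shrinking to 17.2. These bounds assume that every such stop is early and deleted as a failure. If half are early, the figures are 2.6 points and a gap of 18.9. The direction toward methotrexate rests on the SAP's expected rates and equal stop timing, so it is a likely lean and not an established bias.

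It would be wrong to infer that the main result is at risk. ITT is primary and no analysis in the SAP is assigned to the per-protocol set. The consequence would be most serious if that set were used for the non-inferiority analysis. The change should still be made, because this is a named efficacy population and the remedy is small.

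**What to change.** In SAP 4.1:
- Define noncompliance as under 50% of the doses prescribed, at the patient's current protocol dose level and excluding protocol-mandated interruptions, from baseline to the earlier of month 6 or declared treatment failure. This also reconciles the rule with protocol 2.5.3 and removes the problem in step 6.
- State that patients with a declared failure, or scored non-success because of an injection after day 90, stay in the per-protocol set as failures.
- Keep the after-day-90 injection in the SAP 4.2 deviation listing, but not as a ground for exclusion.
- State which analyses use the per-protocol set, and name the population for the non-inferiority analysis in SAP 3.2.2 item 16.

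The cost is a few sentences of SAP text, with no new data or procedures. The downside is that late-injection patients remain in the set, so it is a less pure group of patients treated as planned. The SAP 3.5.1 sensitivity analysis already examines how scoring them differently changes the result.

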4.2 Major protocol deviations

The incidence of deviations from the inclusion and exclusion criteria will be summarized using counts and percentages, and the treatment groups compared for the overall frequency of deviations using a $2 \times N$ Fisher's exact test. Similar deviations will be grouped into general categories of deviations for a more condensed summary. A listing of deviations by participant will also be produced. Any major deviations from the protocol will be listed and/or summarized, including, but not limited to, participants who:

- never received study drug
- were subsequently found to be ineligible for the study
- never returned for a follow-up visit
- have follow-up visits outside the prescribed visit window
- received a corticosteroid injection >90 days after enrollment for macular edema or at any time for inflammation

The number and percentage of randomized participants actually receiving study medication, permanently discontinuing study drug (subdivided by reason), and receiving injections >90 days past enrollment will be summarized. A summary of study participants randomized by site will also be provided. Treatment groups will be compared for the proportion and reason for study drug discontinuation using the chi-square test. A summary of participant status at the end of the study period will also be generated with categories including lost to follow-up.

5 Data Collection and Quality Assurance

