4.1. Visit schedules

4.1.1. Phase I: First-line treatment

After eligibility has been evaluated and informed consent given for participation in the trial, patients will be randomized to receive oral methotrexate or mycophenolate mofetil. Patients will continue with this course of treatment unless treatment failure occurs due to safety, intolerability or lack of efficacy. If a failure is recorded within the first 6 months, the treatment assignment will be switched to the drug not initially randomized to, and the patient will follow a new visit schedule.

Patients who are treatment failures in Phase I due to safety (i.e. a serious adverse event deemed to be related to the study drug by the Medical Monitor) may or may not proceed to

Phase II depending on the Medical Monitor’s determination. In most cases of an SAE, the patient will likely not be allowed to switch to Phase II, but in some cases, such as an SAE due to intolerability, it may be deemed safe to switch to Phase II. Even if the patient does not switch to Phase II, outcome data at 6 months should be collected if the patient is willing.

Treatment success, according to the primary endpoint, will be assessed at 6 months. If treatment has been deemed successful for a patient at 6 months, they will be provided study medication for an additional 6 months and return for additional study visits as shown below. As long as the patient stays on the first randomized medication, Visit Schedule I will be followed.

Guidelines for Visit Schedule I

- Day 1 corresponds to the Baseline-I visit, which is also the first day the patient receives treatment.
- Visit windows are determined based on the date of randomization.
- The baseline eye exam and other baseline assessments may be collected at a separate visit up to 14 days before the patient is enrolled and randomized. Laboratory measurements may be collected within either 4 weeks or 90 days prior to the date of randomization, depending on the laboratory test.
- There should be a minimum of 2 weeks between each study visit.
- Data for the baseline and follow-up visits may be collected anytime within the visit window.

Table 9: Visit Schedule Phase I (0-6 months) or Phase II

Visit	Window Days/Weeks
Baseline*	
Week 2	±3 days
Month 1*	±15 days
Month 2	±15 days
Month 3	±15 days
Month 4	±15 days
Month 5	±15 days
Month 6	-15 to +30

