*Every monthly visit scheduled will be calculated from the baseline visit date (Phase 1), using the average amount of days per month. If a patient does not come in within the visit window, every attempt should be made to get them in for a clinic visit as soon as possible.

Table 10: Visit Schedule Phase I (6-12 months)

Visit	Window (Weeks)
Month 9*	±15 days
Month 12*	-15 to +30

* Since baseline/treatment administration (Phase 1)

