4.4. Follow-up visits

It is strongly encouraged for all follow up data to be collected within the study visit window, but should be collected regardless.

All Phase II procedures and protocol are the same as Phase I. For Phase I patients who are continuing on the same medication, physicians can see the patients as often as they would like. However, for purposes of this study we will only be recording information at Month 9 and Month 12, or a non-study visit that leads to treatment failure.

Laboratory test results will be collected monthly.

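### SAP 4.2 with 4.1, read literally, drops a patient from the per-protocol population for any out-of-window follow-up visit, not only the month-6 endpoint visit

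*Combined protocol and SAP*

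**What the plan says.** SAP 4.1 defines the per-protocol efficacy population as the intent-to-treat population "excluding patients with any of the following: (a) major protocol deviations", or with less than half of the study drug taken. Of the intent-to-treat population it says: "This is the primary population for the efficacy analyses".

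SAP 4.2 introduces its list with "Any major deviations from the protocol will be listed and/or summarized, including, but not limited to, participants who", and one entry is those who "have follow-up visits outside the prescribed visit window". The entry has no threshold, no visit type and no size of departure. Another entry covers patients who never came back for any follow-up. Missing one visit is not listed.

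On the protocol side, section 4.4 reads: "It is strongly encouraged for all follow up data to be collected within the study visit window, but should be collected regardless". The note under Table 9 in section 4.1.1 adds: "If a patient does not come in within the visit window, every attempt should be made to get them in". The windows are in "Table 9: Visit Schedule Phase I (0-6 months) or Phase II": ±3 days at Week 2, ±15 days at Months 1 to 5, and -15 to +30 days at Month 6. SAP 3.2.1 has its own rule for endpoint data: "Data will be included for all outcomes within the window period of -2 weeks to +4 weeks around the 6 Month Visit date".

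**The concern.** A per-protocol set is meant to hold patients who were treated and measured closely enough to plan for the month-6 result to reflect the assigned drug. A visit-timing rule serves that purpose at the visit where the endpoint is read. At the other visits it does little.

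Week 2 has the narrowest window and does not determine month-6 success. The form schedule in protocol 4.2 shows no clinical eye exam form at Week 2, although SAP 3.1 does list inflammation measurements then. A patient seen four days after the nominal Week 2 date, who then stayed on drug and was examined on time at month 6, would still be removed. A patient who skipped Week 2 entirely would not be removed by anything on the list, so attending late is treated more harshly than not attending.

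At stake is the size of the per-protocol set, and with it the precision of any analysis run on it.

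**Working it through.** **Inputs.** Follow-up visits to month 6 (protocol Table 9): Week 2 plus Months 1, 2, 3, 4, 5 and 6, so 7. Planned size (SAP 3.4.1): 108 per arm, 10% loss, success 0.4 against 0.6, two-sided alpha 0.05, power 80%. The documents give no rate *q* of out-of-window visits. I assume 2%, 5% and 10%, equal across visits and independent.

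**The plan's own figure.** SAP equation (5): 2N = 4 × (1.960 + 0.842)² × 0.5 × 0.5 / 0.2² = 196.2. Allowing for 10% loss gives 196.2 / 0.9 = 218.0, or 196.2 × 1.1 = 215.8; both are close to the stated 216. A two-proportion calculation gives 97 per arm, and 97 / 0.9 rounds up to 108. The sample size is not in dispute. It supplies the base of 108 × 0.9 = 97.2 evaluable patients per arm.

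**Share excluded.** If one out-of-window visit among seven suffices, the share is 1 − (1 − q)⁷. If only the month-6 visit counts, it is q.

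**Patients left and power.** n = 97.2 × (1 − q)⁷ or 97.2 × (1 − q) per arm. Power = Φ{[0.2 − 1.96 × √(2 × 0.5 × 0.5 / n)] / √[(0.4 × 0.6 + 0.6 × 0.4) / n]}, taking exclusions as equal in both arms. With no exclusions (n = 97.2) power is 80%.

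| Assumed q | Excluded, any of 7 visits | Left per arm | Power | Excluded, month 6 only | Left per arm | Power |
|---|---|---|---|---|---|---|
| 2% | 13% | 84.4 | 74% | 2% | 95.3 | 79% |
| 5% | 30% | 67.9 | 65% | 5% | 92.3 | 78% |
| 10% | 52% | 46.5 | 49% | 10% | 87.5 | 76% |

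**The two month-6 windows.** Table 9 allows -15 to +30 days. SAP 3.2.1 takes data from -2 to +4 weeks, which is -14 to +28 days. A visit at day -15, +29 or +30 is inside the protocol window but outside the SAP's data window, so any rule tied to month 6 has to say which one it uses.

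**The case against.** The strongest reply is that little depends on this. The efficacy population is intent-to-treat and the primary analysis is complete-case (SAP 3.5 and 4.1), so the item does not touch the main result. The per-protocol population is defined in SAP 4.1, but no analysis in SAP 3.2 is assigned to it. That stands, and it limits the point to the per-protocol set.

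A second reply is that the SAP never says one visit is enough: it uses the plural, in an open list of things to be reported. That is fair as to intent. But SAP 4.1 turns any major deviation into an exclusion, and nothing in either document supplies a threshold or separates major from minor window departures.

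A third is that one common rate does not fit the schedule. With months averaging about 30.4 days and windows of ±15 days, Month 1 runs from about day 15.4 to 45.4 and Month 2 from about 45.9 to 75.9. A late monthly visit therefore soon falls in the next visit's window, and how it would be labelled is not stated. This also stands: the percentages are illustrations, not forecasts.

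Two stronger readings are tempting.

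- **That the protocol and SAP contradict each other on late visits.** They do not. The protocol strongly encourages in-window visits. Collecting late data for the intent-to-treat and safety analyses is compatible with recording a deviation.
- **That the per-protocol set is selected on the primary outcome**, because successes have Months 9 and 12 still to come and switchers have a further seven visits. At q = 5% that gives 1 − 0.95⁹ = 37% against 1 − 0.95¹⁴ = 51%. The 14-point gap needs failure exactly at month 6. Failure at month 3 means 4 + 7 = 11 visits and 43%; failure at month 1 means 2 + 7 = 9 visits and no gap. It also needs later visits to be applied backwards to the month-6 analysis. SAP 3.11 schedules the Aim 1 primary analysis once month 6 and its window are complete, and nothing says a late month-9 visit changes that set.

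**Conclusion.** The point holds for the per-protocol population only. As written, SAP 4.2 with 4.1 excludes patients for visit timing that has no bearing on whether the month-6 outcome was validly measured. The consequence is avoidable loss of precision in any per-protocol analysis. Under the assumed rates, power for the design difference falls from 80% to between 74% and 49%, against 79% to 76% if only month 6 counts. These figures rest on equal and independent out-of-window rates over seven visits, on a single such visit sufficing, and on exclusions spread evenly over the arms. The documents support no particular rate. Neither a conflict between the documents nor bias through selection on the outcome is shown. The change is worth making because it is cheap and the rule as written yields a worse analysis set.

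**What to change.** In SAP 4.2, limit the item to a month-6 endpoint visit of the relevant phase (Phase I for Aim 1, Phase II for Aim 2) made outside the data-inclusion window. State one window, after reconciling the -15 to +30 days of protocol Table 9 with the -2 to +4 weeks of SAP 3.2.1.

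State that patients already declared treatment failures before month 6 are not excluded under this item. Their outcome is already defined: protocol 2.5.1 requires no earlier failure for safety, tolerability or futility, and SAP 3.2.2 scores discontinuation for intolerance or adverse events as 0. For the same reason, do not extend the item to month-6 visits that were not made. That would remove early failures who did not return and push per-protocol success rates upward.

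List all other out-of-window visits as minor deviations that do not affect the per-protocol population.

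The cost is a few lines of SAP wording, one decision on the window and a longer minor-deviation listing. No new data are needed.
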